8.4.3 Surgical Lymph Node Identification

1. If a dye (e.g., VBD or ICG) is to be used, it should be injected according to the standard practice of the clinical site.
2. On entering the subcutaneous tissue, a dye-containing lymphatic vessel or lymph node may be seen. If a dye-containing lymphatic vessel is seen, carefully trace it to the proximal LN. In vivo counts should be recorded and LN removed.

OR

If no dye-containing lymphatic vessel or lymph node is seen, then using a combination of visualization and the handheld gamma detector, explore the lymphatic basin for the LNs. As dissection proceeds towards the LN, repeated use of the handheld gamma detector is helpful in maintaining a line of site to the lymph node. The count rate will increase as dissection approaches the Lymphoseek-containing lymph node(s).

3. Once a LN has been identified, in vivo counts should be taken prior to excision. In vivo counts will consist of a set of three 2-second counts or one 10-second count (depending on the device) over the lymph node. Determination of a positive finding (i.e., localization) is based on the **In Vivo** definition above. Any LN count not meeting this threshold criterion will be considered a negative (non-localized) finding.
4. The method used to identify all LN(s) will be recorded (i.e., dyed appearance, Lymphoseek positive finding, or both) prior to excision.
5. To confirm the in vivo procedure, a set of three 2-second counts or one 10-second count will be recorded for the excised lymph nodes. The mean count of the ex vivo LN will be compared to the mean of normal tissue background counts, and the threshold criterion used to determine a positive finding for the in vivo LNs will be applied to the ex vivo specimens. The appearance and time of excision of the lymph node will be documented. Determination of a positive finding (i.e., localization) is based on the **Ex Vivo** definition above. Ex vivo counts must be performed on all excised lymph nodes

Table 3 describes the procedures that should be followed based on the in vivo and ex vivo status of the tissue that has been excised.

Table 3. Handling of Excised Tissue

In Vivo Assessment	Ex Vivo Assessment	Procedure
Radioactive Status		
positive (hot)	positive (hot)	Send to pathology for further evaluation.
positive (hot)	negative (not hot) or no counts obtained	Incorrect node harvested. Send to pathology for further evaluation. Return to resection bed.
negative or no counts (not hot)	positive (hot)	Comment on why lymph node was removed. Send to pathology for further evaluation.
Dye Status		
dye-identified node	N/A	ANY dye-identified node is sent to pathology for further evaluation regardless of radioactive status.

6. A thorough evaluation of the remaining lymphatic basin should be undertaken since more than one LN may be found. This evaluation should include a combination of palpation, visualization, and gamma detector survey for evidence of dye and/or increased gamma detector count rates.
7. Probing of the area will be complete when all selected node counts are negative by use of the threshold criterion. The surgeon will continue with visualization and palpation according to local practice to ensure that no grossly positive LNs remain at the site of resection.

If a subject has neither a dye-identified node nor any “hot” nodes, continue with visualization and palpation according to your medical expertise.

Pelvic lymphadenectomy will be performed in accordance with institutional standards. Additional surgical intervention such as radical hysterectomy should be performed in accordance with the subject’s surgical plan and the discretion of the surgeon.

All removed LNs (SLNs and NSLNs) must be sent to pathology for using the minimum requirements of histopathological evaluation outlined in the trial pathology manual.

For the purposes of analysis, a sentinel lymph node is defined as being hot ex vivo (lymph nodes with counts above the 3σ rule threshold).

8.5 Histopathology of Lymph Nodes

8.5.1 Local Lymph Node Evaluation

Institutions with SLN ultra staging protocols in place as the standard of care will not be required to deviate from their methods when the minimum recommendation of the trial pathology manual have been met. Institutions that do not routinely employ ultra staging in the assessment of SLNs will be required to assess SLNs in accordance with the trial pathology manual as a minimum. The pathological evaluation of SLNs will include at a minimum serial sectioning and staining (H&E and if negative IHC additionally). The pathological evaluation of NSLNs at a minimum will include bifurcation and staining with H&E. Minimum requirements for fixation, sectioning and staining are outlined in the trial pathology manual.

Final pathology results must reflect consistent numbering and labeling from intraoperative worksheets to the final report. SLNs must be individually identified in the final pathology report.

The pathology evaluation of each node shall be reported as follows:

- A - Macrometastases (> 2 mm)
- B - Micrometastases (≤ 2.0 mm and ≥ 0.2 mm)
- C - Isolated tumor cells or < 0.2 mm

D - No observable tumor presence

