2.2 Secondary Objectives

Estimation of sensitivity, negative predictive value, and overall accuracy of Lymphoseek-detected SLNs relative to the pathology status of non-SLNs.

Estimation of the detection rate of SLNs by Lymphoseek and the rate of tumor detection in non-SLNs.

Determination of the proportion of lymph nodes identified intraoperatively by a dye (e.g., VBD or ICG) that are also identified intraoperatively by Lymphoseek (i.e., concordance using the number of lymph nodes stained by the dye as the denominator).

Determination of reverse concordance comparing dye to Lymphoseek (i.e., using the number of lymph nodes identified intraoperatively by Lymphoseek as the denominator).

Comparison of pathologic assessment of the excised lymph node(s) to confirm the presence/absence of tumor metastases for Lymphoseek and dye on a per-subject basis.

Comparison of imaging and surgical findings.

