3 OVERVIEW OF METHODOLOGY AND DESIGN

3.1 Overall Study Design

This study is a prospective, open-label, within-subject study of Lymphoseek in the detection of lymph nodes in subjects with known cancer of the cervix. The pathology status of non-SLNs in the pelvic lymphadenectomy will serve as the control. All subjects will receive a single dose of 50 µg Lymphoseek (2.0 mCi) prior to ILM. A sample size of 40 was selected in order to provide exploratory results for the primary and secondary objectives. The proposed study includes 3 visits: A screening visit for initial determination of eligibility and evaluation of clinical status (up to 30 days before injection), a baseline visit on the day of surgery, and a 24 ± 12 hour (telephone) safety follow-up.

The Schedule of Events (see [Appendix 1](#)) contains a list of all study procedures and time points. Study activities are described in detail in [Section 7](#).

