4.4 Replacement

Subjects will be replaced under the following conditions:

- Subjects who did not receive study medication or did not proceed to surgery or did not undergo lymphatic mapping with lymph node biopsy.

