9.4 Efficacy Variables

9.4.1 Primary Efficacy Variables

The primary efficacy variable is the per subject false negative rate (FNR), which is the number of subjects with pathologically negative Lymphoseek-identified SLN(s) (or no SLNs were detected) and at least one pathologically positive non-SLN divided by the number of subjects with at least one pathologically positive node (SLN or non-SLN)

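### The control nodes get a lighter minimum pathology work-up than the sentinel nodes, so the false negative rate may be biased low, and no planned analysis addresses it

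*Combined protocol and SAP*

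**What the plan says.** Section 3.1 sets the reference: "The pathology status of non-SLNs in the pelvic lymphadenectomy will serve as the control". Section 8.5.1 sets two different minimum work-ups. For SLNs: "The pathological evaluation of SLNs will include at a minimum serial sectioning and staining (H&E and if negative IHC additionally". For non-SLNs: "The pathological evaluation of NSLNs at a minimum will include bifurcation and staining with H&E". Each node is then graded: A is macrometastasis, B is micrometastasis, C reads "C - Isolated tumor cells or < 0.2 mm", and D is no tumour seen.

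In Section 9.4.1 a false negative subject has no positive SLN (or no SLN detected) and "at least one pathologically positive non-SLN divided by the number of subjects with at least one pathologically positive node (SLN or non-SLN". Section 9.9.3 repeats this as the formula, with an exact two-sided 95% interval, on the ITT set and again on the PP set.

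On dissection, Section 8.4.3 says: "Pelvic lymphadenectomy will be performed in accordance with institutional standards". All removed nodes go to pathology, and Section 4.1.1 requires node dissection in the surgical plan. The analysis rules ask for less. ITT (Section 9.9.1) needs one removed node with histopathology. Section 4.4 replaces subjects who received no study drug or who "did not proceed to surgery or did not undergo lymphatic mapping with lymph node biopsy", so a missing lymphadenectomy alone does not trigger replacement. The NPV and accuracy definitions (Sections 9.4.2 and 9.9.4) score a subject as correctly negative when none of the nodes is positive.

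**The concern.** The numerator of the primary endpoint depends wholly on finding tumour in the nodes that are examined less closely. If disease confined to non-SLNs is missed, a false negative is scored as a true negative. If low-volume disease is found only because SLNs are examined more closely, true positives are added to the denominator. Both lower FNR, so the reported rate mixes tracer performance with work-up intensity. The PP repeat uses the same pathology and cannot show the effect. With so few node-positive subjects expected, one subject's score matters.

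The secondary point concerns NPV and accuracy. A subject whose SLNs were negative but who had no completed dissection would count as a success although nothing verified the result.

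**Working it through.** **Inputs**
- Section 9.7: about 40 subjects, 20% node-positive, expected FNR 12.5%.
- Sections 9.4 and 9.9: FNR = FN/(FN + TP); sensitivity = TP/(FN + TP); NPV = TN/(TN + FN); accuracy = (TP + TN)/N. Intervals below are exact (Clopper-Pearson), 95%.
- Assumption, not in the documents: d is the probability that the minimum non-SLN work-up finds non-SLN-only disease that the SLN work-up would have found.

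**The plan's own figure.** 40 × 0.20 = 8 positive subjects; 8 × 0.125 = 1 false negative. So TP = 7, FN = 1, TN = 32. For 1/8 the interval is 0.3% to 52.7% and half its width is 26.2%. The plan states 26%, so the figure reproduces.

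**Direction, one subject at a time**
- *Non-SLN-only disease missed.* FN becomes TN. FNR goes from 1/8 to 0/7 (0 to 41.0%), sensitivity from 7/8 to 7/7, NPV from 32/33 to 33/33 and accuracy from 39/40 to 40/40.
- *SLN-only disease found only by the closer SLN work-up.* It adds one TP. Without it, 1/8 would be 1/7 = 14.3% (0.4% to 57.9%).
- *Non-SLN disease missed in a subject with a positive SLN.* The subject is a TP either way, so nothing changes.

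None of these raises FNR relative to an equal work-up.

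**Illustrative size, 7 true positives held fixed (ratio of expected counts).** Section 9.7 does not say whether 12.5% assumes an equal work-up or the planned pathology, so both readings are shown.

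| d | If 12.5% is the equal-work-up FNR, expected: d/(7 + d) | If 12.5% reflects planned pathology, equal-work-up FNR: (1/d)/(7 + 1/d) |
|---|---|---|
| 0.9 | 11.4% | 13.7% |
| 0.75 | 9.7% | 16.0% |
| 0.5 | 6.7% | 22.2% |

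**What the recorded grades allow.** Take grade A or B disease in any node as the target, and let any tumour (A to C) in an SLN count as SLN-positive.
- A or B anywhere, tumour in an SLN: TP.
- A or B in a non-SLN, no tumour in any SLN: FN.
- Only grade C anywhere: leaves the denominator.

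If one of the 7 true positives has only grade C disease, FNR is 1/7 = 14.3% (0.4% to 57.9%). If the one false negative has only grade C disease, it is 0/7. The analysis can therefore move either way.

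**Unverified true negatives.** Leaving out one unverified SLN-negative subject takes NPV from 32/33 = 97.0% to 31/32 = 96.9%, and accuracy from 39/40 = 97.5% to 38/39 = 97.4%.

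**The case against.** *The difference belongs to the procedure.* Section 2.1 defines FNR as SLN status relative to non-SLN status in the lymphadenectomy, and Section 8.5.1 openly sets a work-up for each. There is bias only against an equal-work-up target that the plan never sets, and low-volume disease in an SLN is real disease, correctly found. This stands as far as it goes. It is why the claim is relative to an equal work-up and why the primary FNR should stay as it is. It does not remove the need to tell readers that the rate depends partly on unequal examination.

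*The minimums are floors.* Sites may do more, and the pathology manual is not in the documents. This stands: no size can be given, and the d values are not estimates.

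*Grade C.* A reader might infer that grade C is left open, so that the primary result could be chosen after the data are seen. The text does not support that. Section 3.2 speaks of tumour-positive nodes, Section 9.4.2 defines tumour detection through pathologically positive nodes, and only grade D in Section 8.5.1 means no tumour. The Section 2.2 objective "to confirm the presence/absence of tumor metastases for Lymphoseek and dye on a per-subject basis" concerns the comparison with dye and does not define positivity. The natural reading is that A to C are positive; what is missing is one sentence saying so.

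*Dissection.* A reader might also infer that no verifying dissection is required. Sections 4.1.1 and 8.4.3 plan it for every subject, and Section 3.3 demands strict adherence. The gap is only in the analysis rules. The complete-case rule in Section 9.8 might be thought to close it, but it does not say that an undone lymphadenectomy is missing data, and accuracy is divided by all ITT subjects. The PP repeat may drop some such subjects, but a major violation is not defined and ITT is primary.

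*The study is exploratory and unpowered.* This stands: no decision threshold is at stake.

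**Conclusion.** The concern holds in a limited form. At the stated minimums, and relative to an equal work-up, FNR may be biased low and sensitivity, NPV and accuracy high, and no planned analysis addresses this. The direction follows from the definitions. The size cannot be estimated, because the documents give no detection rates and sites may exceed the minimums. On the plan's expected split, one rescored subject moves FNR from 12.5% to 0% or 14.3%, with widely overlapping intervals. The verification gap is real but secondary, at about 0.1 percentage point per subject, and few subjects are likely to be affected. Nothing here shows an error in the sample-size figure. This is a cheap improvement.

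**What to change.** No new pathology is needed.

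1. Keep the primary FNR. State in Sections 9.4.1 and 9.9.3 that grades A to C are pathologically positive for both node types. This is a clarification only.
2. Add one FNR and sensitivity analysis from the recorded grades, scored as in the working: target disease A or B in any node, with A alone as a descriptive row; any tumour in an SLN counts as SLN-positive; subjects with only grade C disease leave the denominator. Do not add a separate version that simply ignores grade C: it would call a subject with C in an SLN and A or B in a non-SLN a false negative, whereas this analysis calls that subject a true positive. State that the analysis reduces denominator inflation but does not recover missed non-SLN disease, and report the unequal minimum work-up as a limitation.
3. For NPV and accuracy, count an SLN-negative subject as a true negative only if the pelvic lymphadenectomy was performed and the removed nodes have histopathology. List the others as unverified and leave them out of numerator and denominator.

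The cost is a few sentences and table rows, assuming the eCRF records whether lymphadenectomy was done (the eCRF is not in the documents). The downside is fewer positive subjects and wider intervals in the added analysis, for example 0.4% to 57.9% for 1/7 against 0.3% to 52.7% for 1/8.

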8.6 Pharmacokinetics

No pharmacokinetic investigation will be performed in this study.

8.7 Safety

8.7.1 Adverse Events

8.7.1.1 Definition of Adverse Event

The definitions below follow International Conference on Harmonization (ICH) – Good Clinical Practice (GCP) (see also ICH Guideline for Clinical Safety Data Management: Definitions and Standards for Expedited Reporting).

Adverse Event (AE)

An AE is defined as any untoward medical occurrence in a subject administered a pharmaceutical product and which does not necessarily have a causal relationship with this treatment. An AE can therefore be any unfavorable and unintended sign (including an abnormal laboratory finding), symptom, or disease temporally associated with the use of a medicinal (investigational) product, whether or not considered related to the medicinal (investigational) product.

By definition for this study, all untoward medical occurrences beginning on the day of injection through the 24 hour post injection assessment are to be reported as AEs. Untoward medical events occurring prior to the day of injection will be captured in medical history. SAEs will be reported from the time of consent through the end of participation.

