6 THERAPIES OTHER THAN INVESTIGATIONAL PRODUCT

6.1 Prior and Concomitant Therapy

All medications taken 30 days prior to Lymphoseek injection through the 24-hour post-injection follow-up will be documented. Any subject that has had preoperative chemotherapy, immunotherapy, or radiation therapy within the 30 days prior to Lymphoseek administration will be excluded from the study.

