7.2.7 Day 1: Imaging and Surgery

SPECT-CT will be performed prior to surgery as described in [Section 8.3](#) and in a manner consistent with the EANM clinical and technical guidelines for lymphoscintigraphy and sentinel node localization in gynaecological cancers as adopted by the SNMMI ([Giammarile et al., 2014](#)). All findings will be documented and recorded on the appropriate case report form (CRF). Dye (e.g., VBD or ICG) may be administered in the operating room immediately before surgical incision. The injection will be performed as deemed appropriate by the surgeon and in accordance with the standard of care at the clinical site. Imaging shall be completed prior to surgery and no greater than 20 hours after Lymphoseek injection, subjects will undergo ILM, SLN(s) will be harvested and surgery to remove the

primary tumor will be completed. Location of both hot and dye-identified nodes will be recorded on the sponsor-provided intraoperative worksheets.

7.2.8 24 ± 12 hours Postsurgical Safety Follow-up (telephone)

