7.2.9 Adverse events and medications will be reviewed. End of Study

The 24 ± 12 hours Postsurgical Safety Follow-up call will serve as the end of study visit. FIGO staging will be reassessed post surgery by the PI and included with the final disposition.

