9.9.5 Safety Analyses

All AEs will be observed for each subject from injection until termination from the study. Additionally, all SAEs will be observed for each subject from time of consent until termination from the study. Prior to analysis, all AEs will be coded using MedDRA. Based on these coded terms, AEs will be summarized using system organ class and preferred term for all subjects in the safety population. AEs will also be summarized by severity, relationship to investigational product, relationship to dye, and relationship to study procedure. All AEs will be listed.

Summary statistics (mean, median, sample size, standard deviation, minimum, and maximum) will be computed on the raw and change from baseline values for each vital sign parameter by timepoint. The pre-injection timepoint will serve as baseline. If there are multiple vital signs taken at any timepoint, then the latest set of vital signs will be used for the analysis. All vital sign data will be listed.

Additional analyses of safety variables for this study may be conducted as described in the Statistical Analysis Plan document.

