Appendix 1 Schedule of Events

Assessment	Screen (Day -29 to Day 0)	Pre- and Post-Injection Day 1 (hour: minute relative to Lymphoseek injection)							Safety Follow- up Call (24 ± 12 hours post-injection)
		-00:10	0:00	00:10 ± 3	0:15	0:30 ± 3	1:00 ± 5	20:00	
Informed Consent	X								
Entry Criteria	X								
Medical History and Demography	X								
ECOG Status & Cancer Staging	X								
Vital Sign Assessment ^a	X	X		X		X	X		
Physical Examination	X								
Review of Medications	X	X							X
Clinical Laboratory Evaluation	X								
Urine or Serum Pregnancy Test ^b		X							
Lymphoseek Administration			X						
Lymphoscintigraphy ^e					X				
VBD or ICG Administration ^c									X
Surgery, Probing and Harvest Lymph Nodes ^d									X
Adverse Event Monitoring		X	X	X	X	X	X	X	X

^a Body weight and height will only be collected at screening

^b Pregnancy testing should be performed within 48 hours before Lymphoseek injection

^c Dye (e.g., VBD or ICG) may be administered immediately before the start of surgery

^d Surgery, node probing and harvesting should occur no later than 20 hours after Lymphoseek injection

^e Lymphoscintigraphy (SPECT or SPECT-CT) should occur between 15 minutes and 20 hours after Lymphoseek injection

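### The one safety call that closes non-serious AE collection is timed from injection in some sections and from surgery in others, so after late surgery it can come too early

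*Combined protocol and SAP*

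**What the plan says.** Several parts of the current protocol text time the last safety contact, and they use different clocks.

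- **From injection.** Section 8.7.1.1 states that "all untoward medical occurrences beginning on the day of injection through the 24 hour post injection assessment are to be reported as AEs". The call column in Appendix 1 is headed "24 ± 12 hours post-injection". Section 6.1 records medications "through the 24-hour post-injection follow-up will be documented".
- **From surgery.** Section 7.2.8 gives the telephone call the same ± 12 h window but counts it from the operation. AEs and medications are reviewed at that call, and section 7.2.9 adds: "The 24 ± 12 hours Postsurgical Safety Follow-up call will serve as the end of study visit".
- **No anchor.** Section 3.1 mentions "a 24 ± 12 hour (telephone) safety follow-up" without saying after what. Section 9.9.5 says "All AEs will be observed for each subject from injection until termination from the study" and gives no time.
- **A further version.** The synopsis describes a follow-up 36 h after injection with vital signs and a physical examination. No other section schedules such a visit.

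Footnote d of Appendix 1 sets the outer limit for the operation: "Surgery, node probing and harvesting should occur no later than 20 hours after Lymphoseek injection". SAEs have a separate rule in 8.7.1.1, running from consent to the end of participation.

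**The concern.** AE incidence is the only safety objective (section 2.3). Section 9.9.5 also summarises AEs by relationship to dye and to study procedure. Dye, when used, is given just before incision, so dye-related and operative events can begin only around or after the start of surgery. A follow-up clock that starts at injection uses up part of its time before those exposures occur, and uses more of it the later the operation starts.

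A site that schedules from Appendix 1 could therefore make its one follow-up call too early to hear about non-serious events after the operation. Events that were never collected cannot be restored at analysis, and section 9.8 rules out imputation. Follow-up after surgery would also differ between sites according to the section they follow, while section 9.3 pools all centres.

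**Working it through.** The plan states no figure to reproduce, so the check is clock arithmetic on its own windows.

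**Inputs**
- S = start of surgery in hours after injection. The lower limit is 1 h (section 8.4.1) and the upper limit 20 h (Appendix 1, footnote d). One synopsis sentence gives 15 h instead; another gives 20 h.
- Appendix 1 call: 12, 24 and 36 h after injection (earliest, nominal, latest).
- Section 7.2.8 call: 12, 24 and 36 h after surgery.
- D = duration of surgery. The documents do not give it. I take D = 0 first, which counts from the start of surgery, and then assume up to 4 h.

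**Step 1: place the Appendix 1 call on the surgical clock.** Relative to the start of surgery it falls at 12 − S, 24 − S and 36 − S hours. With D = 0, the 7.2.8 call is always at 12, 24 and 36 h.

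**Step 2: overlap of the two windows.** The later opening is 12 h and the earlier closing is 36 − S, so the overlap is (36 − S) − 12 = 24 − S hours.

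| S (h) | Appendix 1 call, h from start of surgery: earliest / nominal / latest | Overlap with 7.2.8 window (h) |
|---|---|---|
| 1 | 11 / 23 / 35 | 23 |
| 8 | 4 / 16 / 28 | 16 |
| 12 | 0 / 12 / 24 | 12 |
| 15 | −3 / 9 / 21 | 9 |
| 20 | −8 / 4 / 16 | 4 |

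**Step 3: the threshold.** The earliest compliant Appendix 1 call precedes surgery when 12 − S < 0, that is when S > 12 h. At the same point the nominal call (24 − S) drops below 12 h and so falls before the 7.2.8 window opens. Both stated limits on surgery timing, 15 h and 20 h, allow S > 12 h.

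**Step 4: effect of operating time.** Counted from the end of surgery, the overlap is 24 − S − D. At S = 20 h and D = 4 h it is 24 − 20 − 4 = 0: the windows meet only at 36 h after injection. The nominal call falls before the post-surgical window opens once S + D > 12, which for D = 4 h means S > 8 h. Counting from the start of surgery therefore understates the mismatch.

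**Step 5: can one call break a rule?** Yes. After surgery at S = 20 h, a call 40 h after injection is 40 − 20 = 20 h after the start of surgery. That satisfies 7.2.8 but misses the 36 h upper limit in Appendix 1, although section 3.3 requires strict adherence to the protocol.

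**The case against.** The strongest case for the plan is that nothing has to be lost. Section 8.7.1.1 ends at an assessment, and in the body of the protocol the only later contact is the telephone call with its ± 12 h window. The two windows overlap at every permitted S counted from the start of surgery. Even at S = 20 h, a call at 32 to 36 h after injection meets both definitions. Section 7 also instructs sites, and a site following it reviews AEs at the post-surgical call and loses nothing.

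The schedule also points to same-day surgery. Section 4.1 has subjects arriving on the morning of Day 1, section 7.2.7 puts imaging and surgery on Day 1, and section 3.1 has a single visit on the day of surgery. After a morning injection, S > 12 h means an operation late in the evening or overnight. The two to three days in section 7.1 may simply include the next-day call. Finally, section 8.7.1.4 leaves it to the investigator whether an expected surgical event counts as an AE, so some of these events might go unrecorded under either clock.

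All of this stands, and it limits the size of the problem. It does not say which clock governs.

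A reader might infer two stronger points that the documents do not support:
- **A hard stop at hour 24.** Measured against the earliest post-surgical call, this would give a shortfall of (S + 12) − 24 = S − 12 hours: 3 h at S = 15 and 8 h at S = 20. It sets a nominal time against the edge of a window, and 8.7.1.1 does not name a clock hour as the cut-off.
- **An analysis window in 9.9.5 that contradicts collection.** Section 9.9.5 becomes post-surgical only when read together with 7.2.9. On its own it takes whatever timing the end-of-study call has.

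**Conclusion.** The inconsistency is real, lies in current text, and is minor. The documents allow a loss of non-serious AEs but do not compel it. For same-day surgery the effect is small: with S up to 12 h, counted from the start of surgery, the nominal Appendix 1 call falls within the 7.2.8 window. That assumes calls are made near their nominal time.

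For S > 12 h, an Appendix 1-compliant call can precede the operation or follow it by only hours. At S = 20 h it comes at most 16 h after the start of surgery, against 36 h under 7.2.8. The share of subjects operated on this late is not given and is probably low.

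SAEs are not bound by the post-injection wording, taking the end of participation as the end of study in 7.2.9. The primary false negative rate does not use AE data. The threshold of 12 h rests on counting from the start of surgery and moves down as operating time is added.

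**What to change.** Use one anchor, the end of surgery, wherever the call or the collection period is described:

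- In 8.7.1.1, 3.1, 6.1, the Appendix 1 column header and the synopsis, end AE and medication collection at the telephone call 24 ± 12 h after the end of surgery.
- In 7.2.8, state that the window is counted from the end of surgery. Without this, start and end of surgery remain interchangeable and the window shifts by the operating time.
- For subjects who are dosed but not operated on, time the call at 24 ± 12 h after injection. Section 4.4 replaces them, but section 9.9.1 keeps them in the safety population.
- Delete the 36 h visit from the synopsis.

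Section 9.9.5 needs no change, because it will follow the aligned end of study. Follow-up after injection is not shortened for anyone: the window becomes S + D + 12 to S + D + 36 h, never earlier than the present 12 to 36 h.

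The cost is amendment wording, one column header and the eCRF instruction for AEs and medications. No visit is added, since the post-surgical call already exists in 7.2.8.
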